11.2.2 Secondary and Exploratory Analyses

Details regarding methods for analysis of secondary endpoints will be provided in the Statistical Analysis Plan (SAP). The SAP will also detail the analysis of exploratory and long-term endpoints.

No formal multiple comparisons procedure will be used to control the type I error rate for the analysis of secondary or other exploratory endpoints, including those defined for the long-term open-label phase of the study. For these analyses, confidence intervals and/or p-values will be displayed for descriptive purposes only.

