5.2 SECONDARY OBJECTIVE

To evaluate the efficacy, safety, tolerability and pharmacokinetics of ferric maltol in subject with IDA and CKD over a treatment duration of up to 52 weeks.

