5.4 SECONDARY ENDPOINTS

- Proportion of subjects that achieve an increase in Hb concentration of ≥ 1 g/dL at Week 16.
- Proportion of subjects that achieve a Hb concentration of ≥ 11 g/dL at week 16.
- Change in Hb concentration from baseline to Week 8.
- Proportion of subjects that achieve an increase in Hb concentration of ≥ 2 g/dL at Week 16.
- Change in Hb concentration from baseline to Week 4.
- Changes in iron parameters (ferritin, TSAT, serum iron).
- AEs/SAEs

Additional long-term endpoints up to Week 52/End of Study visit similar to the efficacy and safety endpoints described above.

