11 STATISTICAL CONSIDERATIONS

11.1 SAMPLE SIZE AND POWER CALCULATIONS

A sample size of 135 subjects (Randomized 2:1, ferric maltol:Placebo, 90 in ferric maltol group and 45 placebo) will have 95% power to detect a statistically significant treatment difference of 1.0g/dL between ferric maltol and placebo on the primary endpoint, using a two-sided 0.05 significance level. This calculation assumes a common standard deviation of 1.5g/dl which is based on a pooled estimate of SDs obtained from published trials (Feraheme prescribing information 2010; Quinibi 2011; Macdougall 2014 Schwenk 2010; Singh 2006; Wyck 2005). Assuming a drop-out rate of 20%, approximately 168 subjects total will be recruited. Subjects randomization will be stratified based on baseline Hb value and eGFR.

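### Section 11.2.2 leaves the five double-blind Hb secondary endpoints descriptive; a fixed testing sequence after the primary would allow error-controlled claims at no cost to alpha, primary power or sample size

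*Combined protocol and SAP*

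**What the plan says.** Section 5.3 names one primary endpoint, the Week 16 change in Hb. Section 11.1 sizes the trial for it "using a two-sided 0.05 significance level".

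Section 5.4 lists five further Hb endpoints from the double-blind phase. Two begin "Proportion of subjects that achieve an increase in Hb concentration of", with thresholds of 1 and 2 g/dL at Week 16. The others are Hb of at least 11 g/dL at Week 16, change at Week 8 and change at Week 4. The list order is: 1 g/dL rise, 11 g/dL level, Week 8, 2 g/dL rise, Week 4. Neither section 5.4 nor the synopsis calls this a ranking.

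The secondary objective (section 5.2) begins "To evaluate the efficacy, safety, tolerability and pharmacokinetics of ferric maltol in subject with IDA and CKD".

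Section 11.2.2 defers secondary methods to the SAP but settles multiplicity itself: "No formal multiple comparisons procedure will be used to control the type I error rate for the analysis of secondary or other exploratory endpoints". It adds that confidence intervals and/or p-values for these endpoints are shown descriptively.

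Section 11.2.4 counts subjects who do not return as non-responders for the three responder endpoints. It gives no rule for the Week 4 or Week 8 change.

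**The concern.** The responder and target endpoints are closely tied to the trial's own rationale. Sections 4.2 and 4.5.1 cite 11 g/dL as the guideline target, and section 4.5.1 uses it to justify the entry cut-off. Yet a clear result on the 11 g/dL level, the 1 g/dL responder rate or the speed of response could be cited only as supportive.

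Readers would see up to five unadjusted p-values with no rule to separate a dependable finding from a chance one. Once the single primary test succeeds, its full 0.05 could be passed down a pre-specified sequence. The plan does not use it.

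**Working it through.** **1. The plan's own figure.** Inputs from section 11.1: difference 1.0 g/dL, "This calculation assumes a common standard deviation of 1.5g/dl", 90 v 45 evaluable, two-sided 0.05.

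- Standard error = 1.5 × √(1/90 + 1/45) = 0.274. Ratio = 1.0/0.274 = 3.651.
- Power = Φ(3.651 − 1.960) = 95.5% (95.2% by noncentral t). The plan says it "will have 95% power to detect a statistically significant treatment difference of 1.0g/dL", so this reproduces.
- Dropout: 135/0.80 = 168.75, against "Assuming a drop-out rate of 20%, approximately 168 subjects total will be recruited". This also agrees.

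**2. What a gated sequence does to error.** Test the primary at 0.05. If it is significant, test the secondaries one at a time at 0.05 and stop at the first failure. A false claim requires rejecting the first true null hypothesis in the order. That test is done once, at 0.05, so familywise error over all six tests is at most 0.05. The primary test is unchanged: same alpha, same 95.5%, same 135 evaluable and about 168 recruited. By contrast, a six-way Bonferroni split (0.05/6, critical value 2.638) would cut primary power to Φ(3.651 − 2.638) = 84%.

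**3. Chance findings among five unadjusted tests, with no effect anywhere.**

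- If independent: 1 − 0.95⁵ = 22.6%.
- Simulated with between-visit correlation of 0.3 to 0.8 (assumed): about 17–20% in either direction. About 8–9% of trials show at least one in the drug's favour, against 2.5% for a single test.
- With the gate: about 2% for any secondary claim.

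**4. First step: rise of at least 1 g/dL.** Assumptions: normal changes, SD 1.5, placebo mean change 0, active mean change 1.0, 112 v 56 randomized, 20% counted as non-responders.

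- Placebo: 1 − Φ(1/1.5) = 0.252, times 0.8 = 0.202.
- Active: 1 − Φ(0) = 0.500, times 0.8 = 0.400.
- Pooled rate = (112 × 0.400 + 56 × 0.202)/168 = 0.334. Standard error under the null = 0.0772, under the alternative = 0.0709.
- Power = Φ((0.198 − 1.960 × 0.0772)/0.0709) = 74.5%. With placebo change 0.3 it is 74.9%.

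The endpoint is built from the same Week 16 value as the primary, so requiring the primary to pass first costs almost nothing. Simulation gives 74–76% for passing both.

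**5. Later steps, in the listed order.** The documents give no placebo change, Week 4 or Week 8 effects or SDs, between-visit correlations, or baseline distribution. I therefore used two main sets of assumptions, both at 112/56 with 20% missing at Week 16:

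- Set A: SD 1.5 at every visit, correlation 0.6, baseline uniform 8–11, Week 4 effect 0.3–0.7, Week 8 effect 0.6–0.9, placebo change 0–0.3.
- Set B: baseline mean 10.0 (SD 0.7), Week 4 and 8 effects 0.45 and 0.75 with SDs 0.8 and 1.1, correlations 0.5–0.7, placebo change 0.

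| Passed this step and all earlier ones | Set A | Set B | Range over all runs |
|---|---|---|---|
| Primary | 95% | 95% | about 95% |
| Rise ≥1 g/dL | 74–76% | 74% | 74–76% |
| Hb ≥11 g/dL | 53–56% | 61% | about 53–61% |
| Change, Week 8 | 42–55% | 60% | about 42–61% |
| Rise ≥2 g/dL | 36–47% | 47% | about 36–47% |
| Change, Week 4 | 14–43% | 44% | about 13–46% |

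The last column also covers repeat runs of set B and runs with weaker early effects. With Week 4 and 8 effects of 0.25 and 0.6 and SDs of 1.2 and 1.3, the Week 8 step is 50% and the last step 13%.

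**6. Does the order matter?** Yes. In set B the stand-alone powers are 0.68 for Hb ≥11 and 0.96 for Week 8. In the listed order Week 8 is reached and passed in only 60% of trials. Placed directly after the primary, it passes in about 92%. The Hb ≥11 step is the bottleneck.

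**The case against.** The strongest reply is that nothing here is wrong. There is one primary endpoint with its own alpha, and the secondaries are openly labelled descriptive. This stands.

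A reader might infer that the secondary endpoints can support no conclusion at all, or that the trial's type I error is uncontrolled. The documents support neither. Section 11.2.2 still provides for intervals and/or p-values, the primary error rate is unaffected, and the chance-finding rates in step 3 would mislead only someone who read descriptive p-values as claims.

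It can also be said that the gain is modest. All five endpoints are Hb: three are thresholds on the Week 16 measurement and two are earlier readings. The primary claim does not need them, and the secondary objective promises evaluation, not confirmatory testing. That is fair. It limits the value of the change without making it costly.

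Two further points stand. A reader might take a cost-free sequence to mean that every endpoint keeps its stand-alone power. It does not, because each step needs all earlier ones to succeed. Nor is the section 5.4 order stated to be a hierarchy, so it should not be adopted without thought.

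Deferral to the SAP is a weaker defence. The combined document I worked from contains no separate SAP text, and a hierarchy found only there would contradict section 11.2.2 and need reconciling with it.

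**Conclusion.** The point holds as an improvement that costs the primary analysis nothing, not as the correction of an error. As written, no secondary Hb endpoint can carry a confirmatory claim. With a gated fixed sequence each could, at unchanged primary alpha, primary power and sample size, and anything after the first failure stays descriptive, as it is now.

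The conclusion about error control and cost follows from the design and needs no assumed effects. The size of the gain does need them. Only the first-step figure, about three in four, is stable across the scenarios tried, and it rests on the planning difference and SD, normal changes, placebo change of 0 to 0.3 and 20% non-response. The later figures are ranges under assumptions and should not be read as forecasts.

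**What to change.** For the five double-blind Hb endpoints, replace the sentence in section 11.2.2 with wording such as: if the primary test is significant at two-sided 0.05, the five Hb endpoints are tested in the pre-specified order, each at two-sided 0.05, stopping at the first non-significant result; later p-values are descriptive. Keep iron parameters, exploratory endpoints and open-label endpoints descriptive.

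Three things must accompany it:

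- **Order.** Justify it by clinical priority and power. The section 5.4 order is a possible default, but moving Week 8 ahead of Hb ≥11 g/dL would avoid the bottleneck.
- **Test and missing-data rule for each step.** Section 11.2.4 covers the three responder endpoints. The Week 4 and Week 8 changes need a rule, and all five need a named test.
- **Timing.** Fix all of this before unblinding. Section 8.3 already requires a final SAP before the codes are released for the primary analysis.

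The cost is a short protocol amendment and matching SAP text, somewhat more than one sentence because of the step-level detail. It needs no extra subjects and does not change the primary analysis.

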11.2.3 Sensitivity Analyses

For the primary endpoint, the following sensitivity analyses will be performed:

- The primary analysis defined in Section 12.2.1 (with multiple imputation) will be repeated using the per protocol (PP) population.
- The ANCOVA will be repeated for the ITT population but based on observed data only (complete case analysis without imputation).

- The ANCOVA will be repeated for the ITT population but using last observation carried forward (LOCF without imputation)
- A mixed model for repeated measures (MMRM) ANCOVA will be conducted using observed data only.

Other sensitivity analyses will be documented in the SAP.

11.2.4 Imputation of Missing Data

Missing values for efficacy variables will be replaced for the secondary endpoint analyses as follows:

- For the endpoint 'Increase in Hb concentration of ≥ 1 g/dL at Week 16', subjects not returning to a follow-up visit will be assumed not to have reached the desired concentration.
- For the endpoint 'Hb concentration ≥ 11 g/dL at week 16', subjects not returning to a follow-up visit will be assumed not to have reached the desired concentration.
- For the endpoint 'Increase in Hb concentration of ≥ 2 g/dL at Week 16', subjects not returning to a follow-up visit will be assumed to have not reached the desired concentration.

Safety data will be used according to availability, with no imputation for missing data.

Imputation of missing values for long-term and exploratory efficacy analyses will be defined in the SAP.

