4.4 DOSE SELECTION AND RESULTS OF PREVIOUS CLINICAL STUDIES

Ferric maltol is not absorbed systemically as an intact complex and traditional PK studies may not provide the relevant information (Barrand 1991). Therefore, a model was developed to determine the optimal dose. Data from 6 previous studies of ferric maltol in subject with IBD and IDA were used to estimate absorption rates in the study population. Using these data, the model suggested that in a compliant study population, 30 mg ferric maltol bid would result in correction of baseline anemia in the majority of subjects.

An open-label, randomized Phase 1 study evaluated the pharmacokinetics of ferric maltol and its effect on iron indices in IBD patients with iron deficiency (with or without anemia). Twenty four subjects received ferric maltol 30, 60, or 90 mg bid over an 8-day period. Pharmacokinetics and iron uptake were assessed on Days 1 and 8. Ferric maltol showed predictable pharmacokinetics, with linear increases in exposure, no accumulation over 7 days, and improvements in iron uptake across the dose range 30–90 mg bid.

The dose chosen for Phase 3 studies is 30 mg bid ferric maltol, or 60 mg elemental iron total daily dose.

A Phase 3 study has been completed in subjects with IDA and Inflammatory Bowel Disease (IBD), who are intolerant of oral iron products or are unsuitable for treatment with them (ST10-01-301 and ST10-01-302; Gasche 2014). 128 subjects were randomized to 12 weeks of blinded medication (30mg bid ferric maltol or matched placebo capsule) followed by a 52 week open-label extension period; during which all available subjects received ferric maltol at the same dose. 87% and 82% ferric maltol and placebo treated subjects, respectively, completed the 12 week double blind period. The difference between the treatment groups in mean Hb from baseline to week 12 was 2.25g/dL (ANCOVA $p < 0.0001$). Hb increased to normal values at week 12 in 65% of ferric maltol group and 10% of placebo subjects. When the placebo subjects were transferred to ferric maltol treatment in the open-label phase, there was a sharp rise in Hb levels that mirrored the response in the ferric maltol group in the double-blind phase. There were further increases in Hb up to 48 weeks of treatment and no indication of any reduction in efficacy over the full 64 week treatment period.

Refer to the Investigator Brochure for further information.

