11.2 STATISTICAL METHODS

11.2.1 Primary Endpoint Analysis

Effectiveness will be analysed by determining whether the Test group shows a statistically significant superiority as compared to the Control group.

An Analysis of Covariance (ANCOVA) will be used to analyse the primary endpoint: change in Hb concentration from baseline to Week 16. Missing change from baseline hemoglobin concentration data for week 16 will be imputed using multiple imputation methodology. This will generate 10 complete datasets containing imputed values for those missing in the original dataset. Hb concentrations at baseline, Week 4, Week 8 and gender will be considered as variables helpful in guiding this imputation. For each imputed dataset, the change from baseline to Week 16 complete datasets will be analysed using ANCOVA with factors for treatment and disease and a covariate of baseline hemoglobin and eGFR. By combining the results from these analyses, the treatment estimates will be constructed using the parameter estimates and associated standard errors. Similarly the difference of the adjusted treatment means (ferric maltol – placebo) will be presented with the associated standard error and 2-sided 95 % confidence interval.

The primary endpoint analysis will be performed using the intention-to-treat (ITT) population.

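### Responder endpoints score non-returning subjects as failures while the primary analysis imputes the same Hb value: add an imputed responder analysis, with treatment arm in the imputation model (low priority)

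*Combined protocol and SAP*

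**What the plan says.** Section 5.4 lists three Week 16 responder endpoints: a rise in Hb of at least 1 g/dL, a rise of at least 2 g/dL, and Hb of at least 11 g/dL. For the first and third, Section 11.2.4 states that "subjects not returning to a follow-up visit will be assumed not to have reached the desired concentration"; the rule for the 2 g/dL endpoint is the same in substance.

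For the primary endpoint, Section 11.2.1 states: "Missing change from baseline hemoglobin concentration data for week 16 will be imputed using multiple imputation methodology". It creates 10 datasets and names baseline, Week 4 and Week 8 Hb and gender as variables to guide the imputation. Treatment is named as a factor in the ANCOVA but not as an imputation variable.

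The sensitivity analyses in Section 11.2.3 are for the primary endpoint. Section 11.2.2 leaves methods for secondary endpoints to the SAP, whose text is not in the document reviewed, and makes secondary p-values and intervals descriptive. On expected losses, Section 11.1 says "Assuming a drop-out rate of 20%, approximately 168 subjects total will be recruited", with no split by arm. The only per-arm figures are in Section 4.4, from the earlier study in inflammatory bowel disease: "87% and 82% ferric maltol and placebo treated subjects, respectively, completed the 12 week double blind period".

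**The concern.** Each responder outcome is an exact function of baseline and Week 16 Hb. A subject lost before Week 16 is therefore given a range of plausible Hb values in the primary table and a fixed failure in the responder tables, with no reason stated for the difference.

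Failure scoring mixes Hb response with retention. Whether it understates or overstates the benefit depends on how many subjects are lost from each arm, which is unknown at the planning stage. With only the failure-scored figures, a reader of the responder tables cannot see how much of a difference comes from Hb and how much from completion. At stake are the size and interpretation of three descriptive estimates.

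**Working it through.** **The plan's own figures.** Section 11.1 gives the size and power: "A sample size of 135 subjects (Randomized 2:1, ferric maltol:Placebo, 90 in ferric maltol group and 45 placebo) will have 95% power". The target there is a 1.0 g/dL difference, tested at the two-sided 5% level. On variability the section says: "This calculation assumes a common standard deviation of 1.5g/dl". The noncentrality is 1.0 / (1.5 × √(1/90 + 1/45)) = 3.65, and the noncentral t with 133 degrees of freedom gives 95.2% power. Inflation for drop-out is 135 / 0.80 = 168.75, against about 168 stated. Both reproduce.

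**True responder rates.** Take the change in Hb as Normal with SD 1.5 (protocol) and a difference in means of 1.0 (protocol). The placebo mean change is not given; assume 0.2, so 1.2 on drug.
- Drug: P(change ≥ 1) = 1 − Φ((1 − 1.2)/1.5) = 55.3%.
- Placebo: 1 − Φ((1 − 0.2)/1.5) = 29.7%.
- Difference: 25.6 points.

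**Failure scoring.** If drop-out is unrelated to Hb, the expected scored difference is p_A·c_A − p_P·c_P, where p is the true response rate, c the completion rate, A drug and P placebo.

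| Completion, drug/placebo | Scored rates | Difference (true 25.6) |
|---|---|---|
| 80%/80% | 44.2% vs 23.8% | 20.5 |
| 87%/82% (earlier study) | 48.1% vs 24.3% | 23.8 |
| 75%/90% (assumed) | 41.5% vs 26.7% | 14.8 |
| 85%/70% (assumed) | 47.0% vs 20.8% | 26.2 |

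At 2:1 allocation both assumed splits give 20% drop-out overall: (2×25 + 10)/3 and (2×15 + 30)/3.

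**When it inflates.** The scored difference exceeds the true one only if p_P·d_P > p_A·d_A, where d is the drop-out rate. That requires d_P/d_A > 55.3/29.7 = 1.86. The earlier study's ratio is 18/13 = 1.38, so the effect shrinks. With 13% loss on drug, inflation starts at 13% × 1.86 = 24% placebo loss, that is, below about 76% placebo completion.

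**No drug effect.** With a common true rate p, the spurious difference is p × (d_P − d_A). At p = 29.7% it is 29.7 × 0.05 = 1.5 points at 87%/82%, and 29.7 × 0.15 = 4.5 points at 85%/70%. At 75%/90% it is −4.5 points, favouring placebo. Across p = 25% to 65% the range is 1.25 to 3.25 points at 87%/82% and 3.75 to 9.75 at 85%/70%.

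**Sensitivity to the assumed placebo mean.** With a placebo mean change of 0 the true rates are 50.0% and 25.2%, a difference of 24.8 points. Failure scoring then gives 19.8 at 80%/80%, 22.8 at 87%/82%, 14.8 at 75%/90% and 24.8 at 85%/70%. The small inflation at 85%/70% disappears.

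**Imputed responders, with and without arm.** This was simulated under assumed visit SDs of 1.0, 1.2 and 1.5 g/dL, AR(1) correlation of 0.5 to 0.7, and drop-outs unrelated to Hb and spread evenly over the three intervals. At 13%/18% drop-out the truth is about 25.6 points. Failure scoring gave 23.6 to 23.9, imputation without arm 22.4 to 22.8, and imputation with arm 25.5 to 25.9. At 15%/30%, imputation without arm gave 20.6 to 21.1 and failure scoring 26.2 to 26.3. Leaving arm out pulls the imputed difference toward zero, because subjects lost from either arm are filled in partly from the other.

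**The case against.** Failure scoring is a recognised rule, and it is plausible for part of the loss: falling Hb, transfusion and use of prohibited iron or ESAs are all discontinuation reasons in Section 6.5. The endpoints are descriptive, and Hb itself is examined by multiple imputation, complete-case, LOCF and MMRM analyses. Missing values may also be fewer than the drop-out rate suggests. Subjects who stop treatment are encouraged to attend through Week 16, those who withdraw before then should have the Week 16 assessments done (Section 9.2), and the failure rule refers to not returning rather than to every missing Week 16 Hb. The unseen SAP may add an analysis. All of this stands, and it keeps the priority low. It does not remove the gap: Section 11.2.4 already fixes the rule and names nothing beside it.

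Three stronger readings are tempting and not supported.
- A reader might infer from the earlier study's higher placebo loss that failure scoring will manufacture a benefit here. At those rates and the planned effect it understates the benefit (23.8 against 25.6 points). A difference is created only if the drug has no effect, and it is then about 1.5 points. Those rates also come from 12 weeks in another disease.
- A reader might infer that the trial's type I error or primary result is at risk. The rule does not touch the primary analysis, and no formal claim rests on the responder p-values.
- A reader might take the 20% drop-out as a 20% rate of missing Hb. The documents do not say that.

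**Conclusion.** The inconsistency is real, and resolving it is a cheap improvement of low priority. Failure scoring is not reliably conservative, because its direction depends on drop-out by arm. In the scenarios checked it usually understates a true benefit: by about 2 points at the only per-arm rates in the documents, about 5 at equal 20% loss, and about 11 if drug subjects leave more often (75%/90%). Overstatement needs placebo drop-out nearly twice that on drug, and is 0.6 points at 85%/70%.

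These figures assume normal changes, a placebo mean change of 0.2 g/dL and drop-out unrelated to Hb. The 75%/90% and 85%/70% splits are also assumed. To the extent that those lost are true non-responders, failure scoring is closer to right. The simulated comparison also depends on its assumed visit SDs and correlations.

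**What to change.** Keep the failure rule and add to Section 11.2.4: 'The three Week 16 responder outcomes will also be derived from multiply imputed Week 16 Hb, and the proportions and differences will be pooled and reported beside the failure-scored figures, with missing Week 16 Hb shown by arm and reason.'

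In Section 11.2.1, state that the imputation model includes treatment arm, or is run separately by arm, in addition to baseline, Week 4 and Week 8 Hb and gender. The first change should not be made without the second: with arm omitted, the imputed responder difference was about 20 to 23 points against a true 25.6.

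The cost is a second set of responder figures to report and minor programming on imputed data that the primary analysis already requires.
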